#### 1.51 Clinical Trial Data

As of 18-Oct-2013, 1,000 patients have been treated with MK-3475 at several dose schedules, including 10 mg/kg every 2 weeks. MK-3475 has been generally well tolerated, as expected based on preclinical findings and other anti-PD-1 monoclonal antibodies. As of 18-Oct-2013 no serious infusions reactions have been reported in the first human clinical trial (PN001). Less than 1% of patients thus far assayed had confirmed positive anti-drug antibody (ADA) samples and among these, no or no clear impact on exposure has been observed. There is no contraindication to further clinical investigation with MK-3475.

Pharmacokinetics were as expected, based on MK-3475 being an IgG mAb and based on preclinical data, which support dosing once every 2 or 3 weeks. MK-3475 monotherapy induces an ORR of 25%/27% in patients with ipilimumab exposed melanoma by central independent RECIST and oncology review/investigator assessed irRC, respectively. MK-3475 monotherapy induces an ORR of 39%/43% in patients with ipilimumab-naive melanoma by central independent RECIST and oncology review/investigator assessed irRC, respectively. These responses are remarkably durable.

The preliminary 1-year survival rate for patients, many of whom have had multiple therapies, including ipilimumab, who receive MK-3475 is 81%. MK-3475 monotherapy induces an ORR of 21%/24% in patients with previously-treated NSCLC by central independent RECIST/investigator assessed irRC, respectively, with these responses also remarkably durable. Preliminary data suggest higher levels of PD-L1 expression in tumors of NSCLC are associated with increased activity (ORR 67% by investigator assessed irRC/57% by central independent RECIST); additional data are required to define the optimal PD-L1 cut point. The most commonly reported treatment emergent AEs experienced are fatigue (43.8%), nausea (26.7%), cough (25.3%), pruritus (24.6%), diarrhoea (22.3%) and rash (21.5%). Immune-related adverse events were reported in 21.4% of melanoma patients; most of these events (15.8%) were considered drug-related by the investigator. The most commonly reported immune-related adverse events across the dose-schedules are rash (3.2%), pruritus (2.9%), vitiligo (2.9%), hypothyroidism (2.7%), arthralgia (2.2%), diarrhea (2.2%), and pneumonitis (1.9%). Review of the overall benefit:risk ratio of MK-3475 favors enrollment of eligible patients into clinical trials of MK-3475. The preliminary

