#### 4.0 Test Schedule

##### 4.1 MK-3475 single-agent therapy for both CLL (Arms A and C) and B-NHL (Arm B)

Tests & Procedures	Active Monitoring Phase					
	Days Prior to Registration (Screening phase) ≤30 days	≤14 days	Prior to each cycle, beginning with cycle 2 	Response Evaluation  at 3, 6, and 12 months of therapy	Observation (every 90 days ± 14 days)	At time of progression 
Complete medical history	X					
Adverse event assessment		X	X 	X	X	X
Physical exam, including weight, and vital signs, ECOG PS		X	X 	X	X	X
Height		X				
Tumor measurement by physical exam (CLL/SLL arm only) 		X 	X 	X	X	X
Peripheral blood immunophenotyping by flow cytometry	X 					
CBC with differential and reticulocytes 		X	X 	X	X	X
Serum pregnancy test		X 				
Peripheral smear		X				
Chemistry group (SGOT [AST], SGPT [ALT], total bilirubin[T-Bil], serum creatinine, alkaline phosphatase, direct bilirubin only when T-Bil elevated)		X	X	X	X	X
Uric acid, phosphate, calcium, potassium, sodium		X				
HBsAg, Hep C Ab, HB core antibody		X				
IGHV (CLL/SLL arm only)	X 					
Bone marrow biopsy/aspirate	X 			X 		
Serum protein electrophoresis (SPEP)		X 		X 		

		Active Monitoring Phase				
Tests & Procedures		Days Prior to Registration (Screening phase)	Prior to each cycle, beginning with Cycle 2 	Response Evaluation  : at 3, 6, and 12 months of therapy	Observation (every 90 days ± 14 days)	At time of progression 
		≤30 days	≤14 days			
Beta-2-microglobulin (CLL/SLL arm only)		X				
Serum quantitative immunoglobulins (IgG, IgA, IgM)		X 	X (IgM only) 	X 		X 
Coombs test (monospecific direct coombs IgG and C3)		X				
TSH and Free T4		X		X 		
CD4 T cell number and LDH		X		X		X
CT scan chest, abdomen, pelvis (may use CT portion of the PET/CT) 	X			X		X
Mayo confirmation of tumor diagnosis (NHL arm only) or CLL with Richter/Hodgkin transformation	X 					
Mandatory tissue/node biopsy (see Section 17.0)	X 18, R					X 18, R
Evaluation of MRD by sensitive flow cytometry (CLL/SLL arm only)				X 		

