12. Research bone marrow aspirate specimens must be collected at the same time when clinical bone marrow tests are required (e.g. baseline, 6 and 12 months of therapy or other time when performed) and submitted. If bone marrow was performed prior to consenting the patient for this study, a repeat bone marrow is not required to obtain the research aspirate sample at baseline.
13. Adverse events, CBC, Cr and LFTs must be evaluated every cycle. For patients who tolerated therapy and have clinical benefits, they will be followed at each cycle for the first 6 months. Clinical response will be evaluated at 3 and 6 months. After 6 months of therapy, responsive or stable patients can be followed every other cycle by treating physician/provider until one or two years of total duration of therapy. However, patient will be followed by nurse at each cycle of treatment for adverse event assessment. They will be seen as needed by provider. Physical exam and tumor measurements are required only on cycles where the patient is evaluated by the treating physician. All patients who received at least 6 months of therapy and have shown clinical benefit will be evaluated again at 12 months for clinical response. For patients who continue therapy beyond 12 months, the above schedule is recommended. Further formal response evaluation is only required if there is clinical sign of disease progression. Other response evaluation is per discretion of treating physician.
14. For Follicular lymphoma grade 3 and CLL patients with Richter's transformation or Hodgkin transformation, PET/CT scan will be performed to replace CT at baseline, at 3, 6, and 12 months for response evaluation. Scans after baseline are not required for patients with lymphoplasmacytic lymphoma (Waldenstrom Macroglobulinemia) if utilizing IgM as the criteria for response. If patient had measurable nodes at baseline, then scans should be repeated.
15. For patients with lymphoplasmacytic lymphoma (Waldenstrom Macroglobulinemia) only when this is being used as the criteria for measurable disease.
16. Reticulocytes are required at baseline for all patients. After baseline may be ordered at physician discretion.
17. At 6 month visit. If there is no change from baseline, further testing is not required.

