18. Research tissue/node biopsy- tissue block or slide submission is required for correlative research described in section 17.0. Repeat tissue/node biopsy solely for the purpose of correlative study is not required pre-registration. If a tissue biopsy is done to make a clinical diagnosis per the treating physician, then the tissue block (preferred) or slides should be submitted for correlative research.
19. For Arm A and Arm C patients who go on to combination treatment, this is considered the baseline visit and lab tests before continuing to follow test schedule in Section 4.2.

R Research funded (see Section 19.0). Will be charged to study and not to patient's account.

4.2 Continuation Phase: Combination therapy of MK-3475 with a signal inhibitor (Idelalisib or Ibrutinib) for CLL (Arm A) and CLL with Richter's transformation only (Arm C)

Active Monitoring Phase				
Tests & Procedures	Prior to each cycle, beginning with 2 nd cycle of combination therapy 	Response Evaluation  : at 3, 6, and 12 month of combination therapy	Observation (every 90 days ± 14 days)	At time of progression
Adverse event assessment	X 	X	X	X
Physical exam, including weight, and vital signs, ECOG PS	X 	X	X	X
Tumor measurement by physical exam (CLL/SLL arm only) 	X 	X	X	X
CBC with differential and reticulocytes 	X 	X	X	X
Chemistry group (SGOT [AST], SGPT [ALT], total bilirubin[T-Bil], serum creatinine, alkaline phosphatase, direct bilirubin only when T-Bil elevated)	X	X	X	X
Bone marrow biopsy/aspirate		X 		
Serum protein electrophoresis (SPEP)		X 		
Serum quantitative immunoglobulins (IgG, IgA, IgM)		X 		X
CD4 T cell number and LDH		X		X
CT scan chest, abdomen, pelvis (may use CT portion of the PET/CT) 		X		X
Mandatory tissue/node biopsy (see section 17.0)				X 11, R
Evaluation of MRD by sensitive flow cytometry (CLL/SLL arm only)		X 		
Mandatory blood specimens (see Section 14.0) R	For cycles 2 and 3 of combination therapy and 18 and 24 months of combination therapy 	X 		X 

Mandatory research bone marrow aspirate specimens (see Section 14.0)		X 7,R		
Rochester CLL/SLL Patients Only: Research bone marrow core sample as per 1827-00		X		

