### 7.3 For CLL patients with or without Richter's transformation (Arm A and Arm C), if a patient developed progressive disease (not tumor flare) at any time of the single-agent (MK-3475) therapy, or has stable disease without partial remission at the response

evaluation at month 3 of the single-agent (MK-3475) therapy, a commercially available FDA-approved CLL signal inhibitor can be added to MK-3475 (remain at the dose 200mg IV every 3 weeks). In this clinical scenario, if the patient had not used Ibrutinib in the past, Ibrutinib is recommended to be added using the standard FDA approved dose. However, the dose of Ibrutinib can be modified by treating physician based on concomitant medications or other clinical status. If the patient had progressed or had intolerable adverse events on Ibrutinib, Idelalisib is recommended to be added using the standard FDA approved dose. The dose of Ibrutinib or Idelalisib can be reduced/adjusted due to adverse events or concomitant medications according to the package inserts of the individual agent. If the patient had used both Ibrutinib and Idelalisib in the past, it is at the discretion of investigator/treating physician to decide which FDA-approved oral CLL therapy to use according to the package inserts of the individual agent and clinical status of the patient.

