**7.4 For patient who received ibrutinib previously:**

Note: due to the observed ibrutinib withdrawal syndrome in selected CLL patients who had received ibrutinib before, steroid use in the format of 0.5 mg to 2 mg per kilogram body weight prednisone or equivalent is allowed with a gradual taper to overcome the ibrutinib withdrawal syndrome. The duration of high dose steroid use should be within the first 1-3 months when patients were off ibrutinib

**7.5 If CLL or NHL patients have achieved CMR/CR (MRD negative CR for CLL patients) confirmed by bone marrow or CT/PET evaluation, patients could continue the treatment for 2 more cycles and stop the treatment at the discretion of the treating provider. If patient experiences disease relapse after stopping therapy due to CMR/CR, the previous treatments can be restarted. The designed maximum length of active treatment with MK-3475 is 12 or 24 months.**

**7.6 Total duration of treatment including both single-agent and combination therapy is a maximum of 12 months. If the patient remains on cycles with a length of 21 days without treatment delays, this will be 17 cycles total. If the cycle length is increased due to dosing frequency changes or dose delays occur, the number of cycles will be reduced to not exceed 12 months (365 days) of treatment total. NOTE: If patient is continuing to benefit from treatment after 12 months, they may continue to receive treatment up to a total duration of 24 months including both single-agent and combination therapy at**

investigator/sponsor discretion.

7.7 At the end of the trial therapy with MK-3475, signal inhibitor can be continued or stopped at the discretion of the treating physicians.

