Endocrine disorders	Adrenal Insufficiency Hyperthyroidism Hypothyroidism  Endocrine disorders - Other, Hypopituitarism, Thyroiditis, Hypophysitis  Grade 2	MK-3475	Monitor hormonal levels in the appropriate frequency by the discretion of treating physician until returned to baseline values. Hormonal replacement or other necessary therapy is recommended. Consider endocrine consultation as needed. Hold treatment until AE improves to grade 1 or baseline. If AE improves to grade 1 or baseline within 4 weeks, study treatment should be restarted at the same dose with the same cycle length for the first occurrence. The cycle interval will increase by one week for each occurrence of the same adverse events. If the treatment is delayed $\geq 8$ weeks, study treatment should be discontinued and go to observation if $\geq 2$ cycles of therapy were given, otherwise go to event monitoring.
	$\geq$ Grade 3		Hold study treatment, consider endocrine consultation and discussion. Rule out infection and sepsis with appropriate cultures and imaging. Consider treatment with corticosteroids 1 to 2 mg/kg daily. When symptoms improved to grade 1 or less, steroid taper may be started. Replacement of appropriate hormones may be required. Discuss with study chair for the option of continuation of treatment when the AE improves to grade 1 or baseline within 8 weeks from last therapy. If treatment is discontinued, go to observation if $\geq 2$ cycles were given, otherwise go to event monitoring.

→ → Use the NCI Common Terminology Criteria for Adverse Events (CTCAE) version 4.0* unless otherwise specified ← ←			
CTCAE System/Organ/Class (SOC)	ADVERSE EVENT (at least possibly related)	AGENT	ACTION**
AT TIME OF RETREATMENT			
Eye disorders	Uveitis Grade 1- 2	MK-3475	Hold treatment. Evaluation by an ophthalmologist is strongly recommended. Infectious causes will need to be ruled out. Treat with topical steroids is recommended. For the first occurrence, if AE resolves within 4 weeks, study treatment should be restarted at the same dose with the same cycle length. If AE resolves between 4-8 weeks from the last therapy, the cycle interval will increase by one week. Discontinue treatment if symptoms persist despite topical therapies. Discontinue treatment for the second occurrence. If the treatment is delayed $\geq$ 8 weeks, study treatment should be discontinued and go to observation if $\geq$ 2 cycles of therapy were given, otherwise go to event monitoring.

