**Common known potential toxicities,  $\geq 1$  to  $< 10\%$ :**

Blood and lymphatic system disorders: anemia

Immune system disorders: infusion related reaction  
Endocrine disorders: hyperthyroidism, hypothyroidism  
Metabolism and nutrition disorders: decreased appetite  
Nervous system disorders: headache, dizziness, dysgeusia  
Respiratory, thoracic, and mediastinal disorders: pneumonitis, dyspnea, cough  
Gastrointestinal disorders: colitis, vomiting, constipation, dry mouth  
Skin and subcutaneous tissue disorders: severe skin reactions, vitiligo, dry skin, erythema  
Musculoskeletal and connective tissue disorders: arthralgia, myositis, musculoskeletal pain, pain in extremity  
General disorders and administration site conditions: asthenia, edema, pyrexia, influenza like illness, chills  
Investigations: alanine aminotransferase increased, aspartate aminotransferase increased, blood alkaline phosphatase increased, blood creatinine increased

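### Table 4.2 leaves out TSH/Free T4, so Arm A and C patients who add ibrutinib or idelalisib by month 3 continue MK-3475 with no scheduled on-treatment thyroid test

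*Combined protocol and SAP*

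**What the plan says.** In Section 4.1 the row "TSH and Free T4" is marked in two columns: screening (within 14 days before registration) and Response Evaluation. Footnote 17 limits the second mark: "At 6 month visit. If there is no change from baseline, further testing is not required". The per-cycle, observation and progression columns are blank for this row.

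Section 7.3 lets an Arm A or C patient add a signal inhibitor after progression at any time on single agent, or for stable disease at the month-3 evaluation. MK-3475 continues at the same dose and interval. Footnote 19 of Section 4.1 makes the progression visit the combination baseline "before continuing to follow test schedule in Section 4.2".

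Section 7.6 sets the default limit: "Total duration of treatment including both single-agent and combination therapy is a maximum of 12 months". Extension to 24 months in total is allowed at investigator/sponsor discretion.

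Section 15.17 lists "Endocrine disorders: hyperthyroidism, hypothyroidism" among the common toxicities of MK-3475 (at least 1% and below 10%). For grade 2 endocrine events, Section 8.3 says: "Hold treatment until AE improves to grade 1 or baseline".

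**The concern.** The protocol requires one on-treatment thyroid test for MK-3475. Patients who add a second drug stay on MK-3475 but lose that test, and no reason is given. It looks like a row that was not carried over when Table 4.2 was written.

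Two things are at stake, both limited to grade 2 or higher thyroid events that symptom assessment does not pick up:

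- **Patient management.** The grade 2 hold in Section 8.3 cannot be applied to an event nobody has detected.
- **Safety reporting.** Safety of the combination is a secondary objective (2.24), and Section 16.328 tabulates adverse events separately for single agent and combination. Patients who reach month 6 on single agent get a thyroid test and early switchers do not, so endocrine rates on the combination may be under-counted.

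Grade 1 findings do not enter the argument, because Section 10.61 does not require them to be submitted in either phase.

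**Working it through.** The plan states no figure to reproduce. The check compares the two schedules, then works out the timing and a rough size.

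**1. The two schedules compared.** Table 4.1 has 16 rows with at least one mark after baseline. Table 4.2 carries over 15 of them, and the missing one is TSH/Free T4.

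| Possible place for a thyroid test | Section 4.1 | Section 4.2 |
|---|---|---|
| Screening | yes | not applicable |
| Prior to each cycle | no | no |
| Response evaluation | month 6 only (footnote 17) | no row |
| Progression (combination baseline, footnote 19) | no | no |
| Inside the chemistry group | no | no (liver tests, creatinine, alkaline phosphatase only) |
| Every-cycle laboratory footnote | no (footnote 13) | no (footnote 8: blood count, creatinine, liver tests) |

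**2. Any other source of a test.** Two other places mention hormone testing, and neither schedules it. The endocrine row of Section 8.3 calls for hormone monitoring once an event has been recognised. Section 15.196 calls for laboratory tests as the physician orders when a patient reports symptoms.

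**3. Timing.** Section 11.0 places the month-3, month-6 and month-12 evaluations at the ends of cycles 4, 9 and 17. With 21-day cycles:

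- 4 × 21 = day 84; 9 × 21 = day 189; 17 × 21 = day 357, as the protocol states.
- A month-3 switcher leaves schedule 4.1 at 189 − 84 = 105 days before the only on-treatment test.
- Cycles still possible to month 12: 17 − 4 = 13.
- Cycles still possible to month 24, taking 730 days: 730 / 21 gives 34 full cycles, and 34 − 4 = 30.
- Months still possible: 12 − 3 = 9 by default, 24 − 3 = 21 if extended.

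Progression can trigger the switch at any time, so a patient who switches between month 3 and the month-6 visit also loses the test. Patients who switch after month 6 have already had it.

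**4. Size.** Expected hypothyroidism events = switchers × rate. The documents do not give the number of switchers, so a range is assumed. The ceiling of 44 is all planned accrual in Arm A (23 + 1 = 24) and Arm C (17 + 3 = 20), from Section 16.12. The rates are 2.7% (Section 1.51) and 10% (upper limit of the common band in Section 15.17).

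| Assumed switchers | at 2.7% | at 10% |
|---|---|---|
| 10 | 10 × 0.027 = 0.27 | 10 × 0.10 = 1.0 |
| 44 (ceiling) | 44 × 0.027 = 1.19 | 44 × 0.10 = 4.4 |
| Arm C, 60% of 20 = 12 | 12 × 0.027 = 0.32 | 12 × 0.10 = 1.2 |
| Arm C, 85% of 20 = 17 | 17 × 0.027 = 0.46 | 17 × 0.10 = 1.7 |

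The Arm C rows are a worst case, because adding the inhibitor is optional. All entries count total events, not missed ones.

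**The case against.** The strongest reply is that only one test is lost. Under schedule 4.1 nobody has a scheduled thyroid test before month 6, and an unchanged month-6 result ends testing. A single-agent patient treated to month 24 can therefore go 24 − 6 = 18 months without another. Switchers who stop before month 6 lose nothing, and progression on the combination ends treatment. This stands: the 9 and 21 months describe time without a scheduled test, not the difference between the schedules.

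The event counts can be challenged too. The 2.7% is not restricted by grade or time, and 10% lies just outside the below-10% band. The 44 includes allowances for cancelled and ineligible patients; the evaluable targets sum to 23 + 17 = 40. One test could recover only events present at month 6, of grade 2 or higher, and not already found clinically. The counts are therefore upper bounds, and missed events could be close to none. The documents do not reproduce the CTCAE thyroid grades, so they cannot show how often a grade 2 event would be silent.

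Clinical safeguards also exist. Adverse events are assessed every cycle, Section 15.198 requires fatigue to be assessed before each cycle, and Section 15.196 warns that endocrine problems may show only as vague fatigue. The toxicities listed for idelalisib and ibrutinib include no thyroid disorder. The adverse event analysis is descriptive, with no formal comparison of phases.

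These safeguards reduce the gap but do not close it. Fatigue is listed as a toxicity of all three drugs, and it can also be attributed to the CLL itself (Section 3.13). Section 8.3 asks for no action on grade 2 fatigue but requires a hold for a grade 2 thyroid event. The solicited list in Section 10.6 contains neither fatigue nor an endocrine term. A blood test separates the two explanations where symptoms may not.

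**Conclusion.** The concern holds. TSH/Free T4 is the only post-baseline row of Table 4.1 missing from Table 4.2, and nothing else in the protocol schedules the test. An Arm A or C patient who switches by month 3, or at any point before the month-6 visit, continues MK-3475 with no scheduled on-treatment thyroid test.

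The effect is small: one test per early switcher, plus any repeats that an abnormal result would have prompted. The total-event range rests on an assumed number of switchers and on rates that do not isolate missed grade 2 or higher events. The response-rate decision rules are untouched and the DLT stopping rules essentially so. What suffers is detection of a known toxicity that has its own hold rule, and the completeness of endocrine reporting on the combination. The change is worth making because it is cheap and restores the protocol's own month-6 standard.

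**What to change.** Add a TSH/Free T4 row to Table 4.2. At minimum, require the test at the response evaluation closest to 6 months from the first MK-3475 dose, which is about month 3 of combination for a month-3 switcher. Carry over footnote 17's rule that an unchanged result needs no repeat. Whether to test more often is for the sponsor's clinicians.

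The cost is one table row and one extra laboratory test per switching patient, at an existing blood draw. Arm A closed to accrual in April 2016, so the change applies mainly to Arm C and to any patients still on treatment.

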**5.0 Grouping Factor:**

5.1 Treatment Arm: Arm A (CLL/SLL and CLL with Richter's transformation) vs Arm B (low grade NHL) vs. Arm C (CLL with Richter's transformation)

Note: CLL patients with Richter's transformation or Hodgkin's transformation will be included in Arm A and C.

As per MCCC Addendum 2: An arm (Arm C) with CLL patients with Richter's transformation only is added to the study.

